22 MAR 2021

INCB 54828-201
Protocol Administrative Change 7
Summary of Changes and Rationale

Protocol Title:	A Phase 2, Open-Label, Single-Agent, Multicenter Study to Evaluate the Efficacy and Safety of INCB054828 in Subjects With Metastatic or Surgically Unresectable Urothelial Carcinoma Harboring FGF/FGFR Alterations (FIGHT-201)
Protocol Number:	INCB 54828-201
Protocol Date:	09 MAR 2020 (Amendment 7)
Date of Administrative Change 7:	22 MAR 2021

The primary purpose of this administrative change letter is to eliminate the requirement of survival follow-up for any participants who have documented progression and are no longer receiving treatment with study drug.

This is not a protocol amendment, these changes will be incorporated into a future amended version of the protocol at such a time that an amendment is required.

1. Synopsis; Section 6, Study Assessments (Table 4: Schedule of Assessments); Section 6.4.3, Survival Follow-Up; Section 7.9.2, Data Collection for Survival Follow-Up

Description of change: Long-term survival follow-up for participants with documented disease progression who are no longer receiving treatment with study drug is no longer required.

Rationale for change: Survival outcomes are no longer needed for this study.

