2.2.2. Secondary Endpoints

The secondary endpoints of this study include:

- Objective response rate in subjects with FGFR3 mutations or fusions based on central genomics laboratory results and using an intermittent dose regimen (Cohort A-ID). Response will be based on review of scans by a centralized radiological review committee.
- Objective response rate in subjects with FGFR3 mutations or fusions based on central genomics laboratory results and using a continuous dose regimen (Cohort A-CD) and intermittent dose regimen (Cohort A-ID). Response will be based on review of scans by centralized radiological review committee.
- Objective response rate in all subjects receiving INCB054828 administered as continuous dose regimen and intermittent dose regimen (Cohorts A-ID, A-CD, and B, combined). Response will be based on review of scans by a centralized radiological review committee.
- Objective response rate in subjects with all other FGF/FGFR alterations (Cohort B). Response will be based on review of scans by a centralized radiological review committee.
- Progression-free survival (Cohort A-ID, Cohort A-CD, and Cohort B, separately).
- Duration of response (Cohort A-ID, Cohort A-CD, and Cohort B, separately).
- Overall survival (Cohort A-ID, Cohort A-CD, and Cohort B, separately).
- Safety and tolerability, assessed by monitoring frequency, duration, and severity of

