4.5. Overall Study Duration

The study begins when the first subject signs the study informed consent form. The end of the study will occur when all subjects have discontinued study drug and/or have completed applicable follow-up assessments.

A database lock of the study may occur to allow the analysis of the study data while any enrolled subjects remain ongoing, as long as the Week 21 assessments have been completed for the last subject enrolled. Any remaining subjects may continue to receive study treatment and be seen by the investigator per usual standard of care for this population. The investigator will be expected to monitor for and report any SAEs, AEs of special interest, and pregnancies, as detailed in Section 8. The remaining subjects are considered to be on study until a discontinuation criterion is met and written notification is provided to the sponsor.

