9.4.1.2. Secondary Efficacy Analyses

[figure not shown]
Secondary efficacy analyses will be conducted for the efficacy evaluable population.

Objective response rate for subjects in Cohort A-ID, for subjects in Cohorts A-CD and A-ID combined; for subjects in Cohorts A-ID, A-CD, and B combined; and for subjects in Cohort B will be analyzed in the same fashion as the primary analysis.

Progression-free survival is defined as number of days from the first day of taking study drug dose to the earlier of death or disease progression by RECIST v1.1 as assessed by the centralized radiological review committee. Progression-free survival data will be analyzed by the Kaplan-Meier method for Cohort A-ID, Cohort A-CD, and Cohort B, separately.

Overall survival is defined as the number of days from the first day taking study drug dose to death due to any cause. Subjects without death observed at the time of the analysis will be censored at last date known to be alive. Overall survival will be analyzed by the Kaplan-Meier method for Cohort A-ID, Cohort A-CD, and Cohort B, separately.

The DOR is defined as the number of days from the date of the first confirmed response to the

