#### **2.2.2. Secondary Objectives**

- To evaluate the efficacy of INCB054828 in subjects with advanced/metastatic or surgically unresectable urothelial cancer with different molecular subgroups.
- To evaluate the safety and tolerability of INCB054828.
- To evaluate other clinical efficacy measurements, including duration of response (DOR), progression-free survival (PFS), and overall survival (OS).

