### **2.3.2. Secondary Endpoints**

- Objective response rate in subjects with FGFR3 mutations or fusions based on central genomics laboratory results and using an intermittent dose regimen (Cohort A-ID). Response will be based on review of scans by a centralized radiological review committee.
- Objective response rate in subjects with FGFR3 mutations or fusions based on central genomics laboratory results and using a continuous dose regimen (Cohort A-CD). Response will be based on review of scans by centralized radiological review committee.
- Objective response rate in all subjects receiving INCB054828 administered as continuous dose regimen or intermittent dose regimen (Cohorts A-ID, A-CD, and B combined). Response will be based on review of scans by a centralized radiological review committee.
- Objective response rate in subjects with all other FGF/FGFR alterations (Cohort B). Response will be based on a review of scans by a centralized radiological review committee.
- PFS (Cohort A-ID, Cohort A-CD, and Cohort B, separately).
- DOR (Cohort A-ID, Cohort A-CD, and Cohort B, separately).
- OS (Cohort A-ID, Cohort A-CD, and Cohort B, separately).
- Safety and tolerability, assessed by monitoring frequency, duration, and severity of adverse events (AEs); through physical examinations; by evaluating changes in vital signs and electrocardiograms (ECGs); and through clinical laboratory blood and urine sample evaluations.

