### 7.3.3. Overall Survival

Overall survival is defined as the length of time from the start of the study drug (Day 1) until the date of death due to any cause. Date of death will be determined using the Death Report and the Survival Follow-Up eCRFs. Subjects who are lost-to-follow-up or still alive at the time of analysis will be right-censored at the earlier of the date the subject was last known alive and the clinical data cut-off date for the analysis. The last known alive date is defined as the later of the last study visit and the date the subject was last known alive from the Survival Follow-Up and Subject Status eCRFs.

The number of subjects who died and the number of subjects censored will be summarized. The Kaplan-Meier estimate of median OS will be presented with its 95% CI. The 95% CI will be calculated using the Brookmeyer and Crowley's method ([Brookmeyer and Crowley 1982](#)). The OS analysis will be conducted for Cohorts A-ID, A-CD, and B.

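### Administrative Change 7 ends required survival follow-up for progressed, off-drug subjects, while OS stays a secondary Kaplan-Meier endpoint with no dated cut-off; an OS cut after 22 MAR 2021 would make censoring depend on progression

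*Protocol*

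**What the plan says.** Administrative Change 7 to the protocol, dated 22 MAR 2021, states: "Long-term survival follow-up for participants with documented disease progression who are no longer receiving treatment with study drug is no longer required". The rationale is: "Survival outcomes are no longer needed for this study". The letter post-dates Amendment 7 (09 MAR 2020) and changes the study from then on. It says that it is not itself an amendment and that its content will go into a later version. It lists as affected the Synopsis, Table 4, and Sections 6.4.3 and 7.9.2. The only change it describes concerns follow-up.

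OS by cohort remains a secondary endpoint in Protocol 2.2.2 and SAP 2.3.2. It is analysed by Kaplan-Meier in Protocol 9.4.1.2 and SAP 7.3.3, with planned outputs in SAP Appendix A (Table 2.2.3, Figure 4.2.3).

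On censoring, Protocol 9.4.1.2 says: "Subjects without death observed at the time of the analysis will be censored at last date known to be alive". SAP 7.3.3 censors subjects who are alive or lost at "the earlier of the date the subject was last known alive and the clinical data cut-off date for the analysis", without a calendar date. Protocol 4.5 sets only an earliest lock: a lock is allowed "as long as the Week 21 assessments have been completed for the last subject enrolled".

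The SAP supplied is dated 12 JUN 2019, about 21 months before the letter. Its Section 10.1 records no departure from the protocol's analyses.

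**The concern.** Two things follow from reading these texts together. First, the study says that survival data are not needed and still carries OS as a secondary endpoint. That inconsistency needs no assumption.

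Second, the follow-up rule now differs by progression status. Off-drug subjects without progression stay in disease-status follow-up, which runs to death among other end points (Protocol 6.4.2). Progressed, off-drug subjects have no required contact. Kaplan-Meier needs censoring that is unrelated to the risk of death, and progression is a strong marker of that risk. An OS analysis with a cut-off after the letter would therefore drop from the risk set the subjects most likely to die.

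The estimate at stake is mainly that of Cohort A-CD, the primary-endpoint cohort. Cohort A-ID had to complete enrolment first (Protocol 4.1), and Cohort B closed at Amendment 5 on 18 JUN 2018 (Protocol 6.1), about 33 months before the letter. A reader who sets A-CD beside A-ID descriptively could see a difference that partly reflects the follow-up rule.

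**Working it through.** The plan gives no OS median, event count or follow-up length, so there is no OS figure to reproduce. The size can only be illustrated.

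**Inputs from the documents.** The letter is taken to apply from its date, 22 MAR 2021. The earliest possible start of A-CD is Amendment 5, 18 JUN 2018, which is 33.1 months earlier.

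**Assumptions (not in the documents).** PFS and post-progression survival are exponential, with medians of 4/6, 4/8 or 6/10 months. Ten per cent of PFS events are deaths. Enrolment is uniform. The OS cut is 9 months after the letter. Vital status is complete up to the letter. No deaths of progressed subjects are reported after the letter, or after a safety visit 32.5 days after progression if that is later.

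**Full follow-up.** With λ = ln 2 / median PFS and μ = ln 2 / median post-progression survival:

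S(t) = e^(−λt) + 0.9 · λ/(λ − μ) · (e^(−μt) − e^(−λt))

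For 4/6, λ = 0.1733, μ = 0.1155 and λ/(λ − μ) = 3, so S(t) = 2.7e^(−μt) − 1.7e^(−λt). At t = 11.11 months this is 2.7 × 0.277 − 1.7 × 0.146 = 0.748 − 0.248 = 0.500. The true medians in the three cases are 11.11, 12.97 and 17.61 months.

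**Follow-up under the letter.** The Kaplan-Meier curve estimates the hazard

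h(t) = [0.1λ · N(t) + μ · P(t)] / [N(t) + P(t)]

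where N and P are the unprogressed and progressed subjects still under observation. In the 4/6 case the death rates are 0.1λ = 0.0173 and μ = 0.1155 per month, a ratio of 6.7. Taking subjects out of P therefore lowers h(t) and raises the curve.

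Shift in median OS (months), from simulation of 400,000 subjects per scenario; direct numerical integration of h(t) agrees to within 0.02:

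| Enrolment window, months before the letter | 4/6 | 4/8 | 6/10 |
|---|---|---|---|
| 33 to 20 | 0 | 0 | 0 |
| 33 to 15 | 0 | 0 | +0.04 |
| 33 to 12 | 0 | 0 | +0.17 |
| 33 to 9 | +0.02 | +0.05 | +0.42 |
| 33 to 6 | +0.12 | +0.18 | +0.72 |
| 33 to 3 | +0.30 | +0.36 | +0.95 |
| 24 to 6 (compressed) | +0.19 | +0.30 | +1.37 |
| 50 to 33 (Cohort B timing) | 0 | 0 | 0 |

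The second decimal is given only so that the table can be reproduced. For the 33-to-6 window:

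- **18-month OS** moves from 26.2, 34.2 and 49.0% to 27.6, 35.4 and 50.8%.
- **A cut 3 months after the letter** gives +0.10, +0.12 and +0.33; 18 months after gives +0.12, +0.18 and +0.78.
- **The sampling SD of the median** at n = 100 is 1.2, 1.5 and 2.4 months, so these shifts are below one SD.
- **Sign.** If 30% of the later deaths are reported, the shifts are +0.04, 0.00 and +0.08. At 60% they are −0.03, −0.14 and −0.41, because deaths then enter as events while survivors are censored early.

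**Sensitivity to enrolment near the letter.** A second model used 18 months of enrolment, a cut 12 months after the letter, and median time to progression / post-progression survival of 4/6, 6/9 or 4/12 months. With enrolment ending 12 or more months before the letter, the median moved by at most 0.1 month. Ending 6 months before, it moved from 10.8 to 11.0, 16.3 to 17.4 and 17.1 to 17.6. Ending 3 months before, the largest move was 16.3 to 19.0; ending at the letter, 16.3 to 25.2.

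**Cut on the letter date.** No subject has yet been released from follow-up, so the two follow-up rules give the same curve and the shift from the letter is zero.

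**The case against.** The strongest reply is that the bias is hypothetical. The letter's rationale fits OS having been analysed already, or abandoned, and no passage schedules an OS cut after it. That stands. A reader might infer that the trial's OS result is biased, but the documents do not support this. They show an endpoint that was not reconciled with a follow-up change, and a bias that arises only with a later cut.

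A reader might also infer that the plan has no OS cut-off at all. That goes too far: SAP 7.3.3 names a clinical data cut-off, and only its date and any link to the letter are absent. A SAP of JUN 2019 could not have anticipated a letter of MAR 2021, so its silence was not a fault when written.

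Nor can one say that the letter leaves every OS passage untouched. It lists the Synopsis, which holds the OS objective, endpoint and Kaplan-Meier plan. But the change described is to follow-up only, so this does not show that OS was withdrawn.

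Finally, follow-up is no longer required rather than prohibited, and every survival input above is assumed. Both points stand against quoting any size as a finding about this trial. Neither removes the need for a common cut-off: partial reporting makes even the direction unpredictable.

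**Conclusion.** The point holds in conditional form, and it is minor. The documents establish that survival follow-up was cut back selectively while OS stayed a per-cohort secondary endpoint with an undated cut-off. If OS was cut on or before 22 MAR 2021, the letter causes no bias. If it is cut later and no later deaths of progressed subjects are reported, OS is overestimated, mainly in late enrollees, expected to be Cohort A-CD. Cohort B is essentially unaffected.

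Under the assumed inputs, with A-CD enrolment starting at Amendment 5, the shift in the median runs from 0 (enrolment ended well over 12 months before the letter) to about 1 month. It is about 1.4 months if enrolment was compressed into the window 24 to 6 months before. Enrolment closer to the letter would make it larger. These figures are illustrations, since neither the end of enrolment nor the cut-off is in the documents.

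The consequence is limited. SAP 3.1 calls all analyses exploratory, there is no control arm, and the primary ORR does not depend on survival follow-up.

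**What to change.** In SAP 7.3.3, set one OS cut-off for all subjects, no later than 22 MAR 2021. Use no deaths or follow-up after it in the OS analysis, and record the change in SAP 10.1. If OS was already cut before the letter, stating that date is enough.

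If vital status was not confirmed for all subjects as of 22 MAR 2021, use the last completed survival-contact round before it, based on the interval actually applied. Protocol 6.4.3 asks for contact at least every 12 weeks. Protocol 7.9.2 asks for no longer than 6 weeks for subjects not returning to the investigator, with 12 weeks allowed after the final primary analysis. In the 33-to-6 window, a letter-date cut with status known only from routine contacts leaves +0.04, +0.03 and +0.08 month with 42-day contacts, or +0.09, +0.09 and +0.19 with 84-day contacts. That residue comes from contact lag, not from the letter. Cutting one interval earlier brings the median within 0.02 month of the truth.

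The cost is wording and one date. In the 33-to-6 window, deaths used per 100 subjects fall from 72.5 to 71.2, 65.6 to 64.5 and 53.5 to 51.8, a loss of 1.3, 1.1 and 1.7. The SD of the median does not rise (1.2, 1.5 and 2.2 months). Going back one contact round leaves unused at most about 5 deaths per 100 (6-weekly) or 9 (12-weekly). Reporting OS with a dated cut-off is preferable to deleting a prespecified endpoint after its data have been collected.

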## LIST OF ABBREVIATIONS

| Abbreviation | Term   |
|--------------|--|
| AE           | adverse event                                  |
| BMI          | body mass index                                |
| CI           | confidence interval                            |
| CR           | complete response                              |
| CRF          | case report form                               |
| CSR          | Clinical Study Report                          |
| CTCAE        | Common Terminology Criteria for Adverse Events |
| DOR          | duration of response                           |
| ECG          | electrocardiogram                              |
| ECOG         | Eastern Cooperative Oncology Group             |
| eCRF         | electronic case report form                    |
| FDA          | Food and Drug Administration                   |
| FGF          | fibroblast growth factor                       |
| FGFR         | fibroblast growth factor receptor              |
| MedDRA       | Medical Dictionary for Regulatory Activities   |
| NCI          | National Cancer Institute                      |
| NE           | not evaluable                                  |
| ORR          | overall response rate                          |
| OS           | overall survival                               |
| PD           | progressive disease                            |
| PFS          | progression-free survival                      |
| PP           | per protocol                                   |
| PR           | partial response                               |
| QTcF         | Fridericia correction                          |
| RECIST       | Response Evaluation Criteria in Solid Tumors   |
| SAE          | serious adverse event                          |
| SAP          | Statistical Analysis Plan                      |
| SD           | stable disease                                 |
| SI           | international system of units                  |
| TEAE         | treatment-emergent adverse event               |
| TNM          | TNM Classification of Malignant Tumors         |
| WHO          | World Health Organization                      |

## **1. INTRODUCTION**

This is a Phase 2, open-label, monotherapy study of INCB054828 in subjects with metastatic or surgically unresectable urothelial cancer harboring FGF/FGFR alterations. A detailed description of the investigational product, target patient population, rationale for doses to be examined, and potential risks and benefits of treatment with INCB054828 is provided in Section 1 of the Protocol.

The purpose of this SAP is to provide details of the statistical analyses that have been outlined in the Study INCB 54828-201 Protocol.

## **2. INFORMATION, OBJECTIVES, AND ENDPOINTS**

### **2.1. Protocol and Case Report Form Version**

This SAP is based on INCB 54828-201 Protocol Amendment 6 dated 20 NOV 2018 and case report form (CRF) approved on 03 OCT 2018. Unless superseded by an amendment, this SAP will be effective for all subsequent protocol amendments and eCRF versions.

### **2.2. Study Objectives**

#### **2.2.1. Primary Objective**

- To evaluate the objective response rate (ORR) of INCB054828 as a monotherapy in the treatment of metastatic or surgically unresectable urothelial carcinoma with fibroblast growth factor receptor 3 (FGFR3) mutations or fusions.

#### **2.2.2. Secondary Objectives**

- To evaluate the efficacy of INCB054828 in subjects with advanced/metastatic or surgically unresectable urothelial cancer with different molecular subgroups.
- To evaluate the safety and tolerability of INCB054828.
- To evaluate other clinical efficacy measurements, including duration of response (DOR), progression-free survival (PFS), and overall survival (OS).

## **2.3. Study Endpoints**

### **2.3.1. Primary Endpoint**

- Objective response rate in subjects with FGFR3 mutations or fusions based on central genomics laboratory results and INCB054828 administered using a continuous dose regimen (Cohort A-CD). Response will be based on a review of scans by a centralized radiological review committee.

### **2.3.2. Secondary Endpoints**

- Objective response rate in subjects with FGFR3 mutations or fusions based on central genomics laboratory results and using an intermittent dose regimen (Cohort A-ID). Response will be based on review of scans by a centralized radiological review committee.
- Objective response rate in subjects with FGFR3 mutations or fusions based on central genomics laboratory results and using a continuous dose regimen (Cohort A-CD). Response will be based on review of scans by centralized radiological review committee.
- Objective response rate in all subjects receiving INCB054828 administered as continuous dose regimen or intermittent dose regimen (Cohorts A-ID, A-CD, and B combined). Response will be based on review of scans by a centralized radiological review committee.
- Objective response rate in subjects with all other FGF/FGFR alterations (Cohort B). Response will be based on a review of scans by a centralized radiological review committee.
- PFS (Cohort A-ID, Cohort A-CD, and Cohort B, separately).
- DOR (Cohort A-ID, Cohort A-CD, and Cohort B, separately).
- OS (Cohort A-ID, Cohort A-CD, and Cohort B, separately).
- Safety and tolerability, assessed by monitoring frequency, duration, and severity of adverse events (AEs); through physical examinations; by evaluating changes in vital signs and electrocardiograms (ECGs); and through clinical laboratory blood and urine sample evaluations.

### 3. STUDY DESIGN

This is an open-label monotherapy study of INCB054828 in subjects with metastatic or surgically unresectable urothelial cancer harboring FGF/FGFR alterations. Subjects will receive INCB054828 at a once daily starting dose of 13.5 mg on a 2-weeks-on-therapy and 1-week-off-therapy schedule.

Protocol Amendment 5 introduces a new dose regimen for INCB054828 (13.5 mg continuous dose regimen [no planned dose holiday]). Subjects receiving a continuous dose regimen will be enrolled in a new cohort (Cohort A-CD). *Note:* Subjects enrolled in the current Cohort A (intermittent dose regimen [Cohort A-ID]) will continue to receive treatment with INCB054828 as 2-weeks-on/1-week-off therapy. Subjects in Cohort A-ID will not switch to a continuous dose regimen.

Subjects can enroll if they have a known FGF/FGFR alteration and have either: (a) failed at least 1 previous treatment for their metastatic or surgically unresectable urothelial carcinoma (ie, chemotherapy, immunotherapy) or (b) have not received chemotherapy for metastatic or surgically unresectable urothelial carcinoma due to poor performance status (ie, ECOG performance status of 2) and have insufficient renal function (ie, creatinine clearance < 60 mL/min or local guidelines).

Potential subjects can be screened/enrolled based on local genomic sequencing but must have their tumor samples sequenced through the sponsor's central laboratory. The results from the central laboratory will be considered final. In cases where the central laboratory does not show an alteration, the investigator will decide if continuing treatment is in the best interest of the subject; however, the subject will not be included in the efficacy analyses and may be replaced.

The study will enroll approximately 240 subjects:

[figure not shown]
- Cohort A-ID: FGFR3 mutations or fusions (n = 100); this cohort will complete enrollment before Cohort A-CD begins enrolling subjects.
- Cohort A-CD: FGFR3 mutations or fusions (n = 100).
- Cohort B: all other FGF/FGFR alterations (n = 40).

Once a subject has completed screening and has enrolled into the study, treatment will start on Day 1. Subjects will undergo routine safety assessments during treatment as well as routine efficacy assessments. Subjects will be allowed to continue receiving study drug in 21-day cycles until documented disease progression or unacceptable toxicity is reported.

In addition to introducing continuous dosing, up-titration will be implemented. Any subject who does not reach the target serum phosphate level of > 5.5 mg/dL will increase the daily dose to 18mg.

The overall study design is shown in [Figure 1](#).

